## **Inclusion/Exclusion Criteria**

Inclusion in the study consists of the following criteria:

- Age equal to or above 18.
- Body Mass Index  $\geq 25$ .

Exclusion from the study consists of the following criteria:

- Age equal to or below 17.
- Body Mass Index  $< 25$ .
- Open sores, wounds, or otherwise compromised skin in the treatment area
- History of keloid formation, hypertrophic scarring, or abnormal/delayed wound healing.
- Known or suspected pregnancy, or active nursing.
- General systemic conditions of arteriosclerosis, anemia, aortic aneurysm, or hypertension.
- Liver conditions such as hyperlipidemia, hepatitis, liver disease, or abnormal liver function
- Diabetes or blood-glucose sensitivity
- Any prior invasive cosmetic surgery to the waist or abdominal area, such as liposuction.
- Hernias or diastasis recti within the treatment area.
- Concurrent, or within the last 6 months, participation in any clinical trial for another device or drug.
- Existing bacterial or viral infections (influenza, rhinovirus, hepatitis, pneumonia, tuberculosis, and the like)
- Presence of acne vulgaris, herpes zoster, psoriasis vulgaris, or similar skin conditions in the treatment area.
- Any type of cosmetic treatment to the target area within the last 6 months.
- Implanted active medical device anywhere in the subject, or metallic or polymeric implants in the vicinity of the treatment area.
- Currently undergoing, or recently underwent, chemotherapy or radiation treatment.
- Per the investigator's discretion, any physical or mental condition which may compromise the patient's safety or welfare.
- Failure to complete the study as outlined.

## **Statistical Methods**

Single factor ANOVA analysis will be used to determine if the extent of circumference reduction in the test group is statistically significant over changes in the control group. Additional correlation assessment will be performed to identify any potential relationships between patient data sets, and single-factor ANOVA assessment applied to those correlations as applicable. Missing or incomplete data shall be populated using least-favorable data from participants who did complete the study.

## **Recruitment**

Recruiting shall consist of about 50 patients, with a target of at least 40 patients completing the study. Should patients drop out of the protocol such that 37 patients are not achieved at the end of the study, additional patients shall be recruited to achieve the target number.

## **LIST OF ABBREVIATIONS AND TERMS**

*BMI* - Body Mass Index: A calculation incorporating a patient's height and weight to provide a comparative value on the extent of obesity of the patient.

*RF* - Radio Frequency. In the context of this device, this is radio frequency emissions intended by the product. This feature of the device will not be included in this study.

*US* - Ultrasound

#### **INVESTIGATORS AND ENVIRONMENT OF TREATMENT**

All testing conducted under this investigation will be performed at a single site, an existing dermatology practice located in Midvale, Utah. This setting is representative of the medical office environment under which the device would be used in the market. Consistent with this setting, patients will be scheduled for treatment and upon arrival have the procedure performed, along with appropriate pre-treatment and post-treatment assessment and instructions, and then allowed to depart. The principal investigator for this study has no contractual or financial relationship with the sponsor or with the specification developer. Additional research staff, in the persons of medical staff and assistants already present at the study site, shall assist with the performance of this study. Treatment and measurement activities shall be conducted in separate rooms, and shall be performed by different staff. Assessment shall be performed by licensed physicians.

## INTRODUCTION

The purpose of this study is to evaluate principally the effectiveness, and secondarily the safety, of external application of lower frequency ultrasound to the waist/abdominal region of overweight adults to achieve a reduction of adipose cells/tissues in the subcutaneous region. The application of higher frequency (200kHz to 3MHz) ultrasound for this purpose has been previously demonstrated and such devices have received clearance for treatment. The question remains whether application of ultrasound at a lower frequency (35kHz to 45kHz) can achieve comparable results without introducing any new or elevated risks to the patient. This study seeks to answer this question. Some studies have been published that touch on this question to some extent, but these studies do not take into account variables such as instructions for a healthy lifestyle, or the operation of a device at the intensity levels designed into the Ultimate Contour device.

The proposed clinical mechanism of operation for this device is as follows: High intensity ultrasound energy is applied externally to the outside skin surface. A sonically conductive medium such as an ultrasound-conducting gel or fluid is applied to the skin surface to help avoid air pockets or gaps between the transducer surface and the skin. The ultrasound energy passes through the skin and into the subcutaneous adipose layer, where sonic cavitation occurs. This cavitation disrupts and ruptures cell membranes of the adipose cells. The liberated contents of the adipose cells are then cleared away naturally via the lymphatic system. It should be noted that the purpose of this study is not to verify this mechanism of action, but to validate overall results via assessment of factors that may occur as a result of this theory.

The device in question, presently branded as the Ultimate Contour Mini, is at the stage of development where functional demonstration devices have been constructed and assembled. The design at present is representative of the final released configuration to the extent that third-party safety testing and certification has been conducted on the device and the device demonstrated to be safe relative to the design and constructional requirements of IEC 60601-1 (3rd Edition) for safety of electrical and electronic medical devices and systems, as well as IEC 60601-1-2 (3rd Edition) for electromagnetic compliance safety and performance of electrical and electronic medical devices and systems.

The study has a fixed endpoint of three (3) treatment sessions and three follow-up visits per patient, to the extent that a sufficient quantity of patients have completed the study. Given that a gap of 6-8 days will exist between treatments, the scheduling of patients will be staggered as necessary to best utilize investigator and equipment resources, with the overall course of the study treatments is not expected to exceed 6 weeks of total study time. The follow-up visits are mandated to occur at intervals of one, four, and twelve (12) weeks from the date of final treatment. Once all patient treatments are completed, analysis of the data shall be performed by the sponsor (and reviewed by an independent statistical resource) to determine the extent of success in achieving the primary and secondary objectives.

## **STUDY OBJECTIVES**

**PRIMARY** - The primary objective of this study is to determine if the application of lower frequency (35kHz to 45kHz) ultrasound energy to the waist/abdominal region of the human body is capable of effecting a reduction in the amount of subcutaneous adipose cells and/or tissue to an amount of at least 1 inch and to a statistically significant level. Determination of the reduction in this adipose tissue is achieved via measurement of the body circumference that includes the abdominal area that was treated, and comparing measurements prior to the initial treatment with measurements after the entire treatment regime is concluded. Per the proposed clinical mechanism of action, the disrupted tissue is cleared by the lymphatic system which facilitates excretion or elimination of the disrupted tissue contents. Having been eliminated, the patient should exhibit a reduction in waist circumference. For this objective to be successfully achieved, a reduction in waist circumference of at least one inch must be demonstrated at a point of 12 weeks after the last of three treatment sessions has been applied.

**SECONDARY** - The secondary objective of this study is to assess the safety of this device. Assessment is made by having the patient rate the treatment experience and report any symptoms, side effects, or associated abnormal conditions. Additional assessment is made by the investigators to qualitatively confirm if visually detectable abnormal conditions (example: edema) are presented following the treatment. Success is determined by whether the patients indicate that any discomfort experienced during the treatment, and following the treatment that are directly attributable to the treatment, along with an absence of side-effects or abnormal conditions directly attributable to the treatment, create a risk/benefit condition where the benefit of treatment is regarded to outweigh the risks and temporary discomfort. Quantitatively, the benefit is regarded to outweigh the risk when: 1) No patients report a pain rating of 4 or higher on the Stanford Pain Scale, 2) No patients exhibit any side effects or abnormal conditions at the conclusion of the final treatment, and 3) No patient who was included in the Test group reports that the treatment regimen was unsuccessful.

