### **Methodology**

Samples of the test device (Ultimate Contour Mini by CAO Group, West Jordan, Utah, U.S.A.) will be provided for the test. The devices consist of a touch screen interface whereby the operator may select the intensity of the delivered energy and the duration of treatment. The device features a single output cable to which is attached the ultrasound handpiece assembly. For the purposes of this test, the duration of treatment will be set at 30 minutes, and the intensity set at Level 4 (the maximum the device is capable of).

Application of the ultrasound energy consists of applying a treatment gel or liquid to the patient's skin (to eliminate air gaps between the applicator and the skin) and gently kneading the skin in circular motions, slowly progressing across the surface of the treatment area, making methodical passes until the entire treatment area has been exposed, then returning to the origin point and repeating this application approach.

Following treatment, the patient will be asked regarding the extent of discomfort experienced during the ultrasound application, and assessment will be made by a blinded, independent evaluator whether a number of visible skin conditions are observed or experienced by the patient.

Prior to the first treatment, the patient's weight and height will be measured by the blinded, independent evaluator, and the patient's waist circumference measured using a constant-tension flexible tape measure. Each patient will be treated a total of three (3) times, with a gap of 6-8 days between each treatment. Prior to each treatment, the patient will be weighed. Following the final treatment, the patient will be advised of support mechanisms (healthy diet, exercise, and so forth) to support a successful outcome. At 1, 4, and 12 weeks after the last treatment, the patient will be recalled for a final measurement and review of any outstanding adverse events. Study success shall be determined by achieving at least 1 inch of waist reduction between the initial measurement and the 12-week follow-up.

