### **Study configuration**

This study is designed as a single-arm study. All eligible candidates shall be enrolled to undergo treatment by the device according to the procedure and protocol that are discussed herein. This approach is consistent with other studies that have been done with similar devices where the primary objective of waist circumference reduction was also intended.

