### **Efficacy & Safety variables, including collection of adverse event data and anticipated adverse reactions**

#### **EFFICACY**

Input variables related to the determination of efficacy include the patient's age, gender, ethnicity, height, and weight (to determine the relative extent of obesity). Study output variables collected during this trial included the change in patient waist circumference as a primary indicator. Capture and collection of patient images may be useful for informational purposes, but are not a requirement of this study and shall not be used for any data analysis or study conclusions.

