### **Statistical methods planned, including handling data exclusion, analysis of sub-groups if any**

Any patient that did not conclude all three treatments shall be excluded from the analysis. If there are fewer than 37 patients remaining after the study concludes and exclusions are applied, than no analysis shall take place and additional study subject enrolled until a minimum of 40 completed participants exist. In the event that a patient concludes at least one treatment session, but afterwards discontinues

participation in the study, the presence of the patient in the study shall be acknowledged for data analysis purposes. Missing data for such acknowledged participants shall be fulfilled by inserting the least favorable result obtained realized from among all test subjects who did complete the study. Statistical analysis shall then proceed on the fully populated study data.

Primary analysis shall consist of applying the Anova single-factor acceptance test evaluating the change in waist circumference based on the data collected by the tape measure. A confidence of  $P=0.05$  shall be applied. The results of this data shall be directly applied to determining if the primary objective of the study has been met.

A correlation analysis shall be applied to all variable data recorded, as well as key calculations from the data, to identify any potential two-way connections or relationships between sets of data. Any correlations scoring a magnitude of 0.85 or greater shall be discussed and if appropriate, Anova single-factor analysis applied to determine if there is statistical significance to the relationship and any statements that might be supported by the data. Of primary interest is any impact the starting BMI might have on the amount of change, and any impact that gender may impart to the outcome.

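### The primary success rule is stated in three forms, and none says which quantity must reach 1 inch; the stated 80% power covers significance only

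*Combined protocol and SAP*

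**What the plan says.** Three places decide whether the trial has succeeded.

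- **Synopsis, Methodology:** "Study success shall be determined by achieving at least 1 inch of waist reduction between the initial measurement and the 12-week follow-up". Significance is not mentioned.
- **STUDY OBJECTIVES, primary:** the reduction must be shown "to an amount of at least 1 inch and to a statistically significant level", and "a reduction in waist circumference of at least one inch must be demonstrated at a point of 12 weeks" after the last treatment. The method is described as "comparing measurements prior to the initial treatment with measurements after the entire treatment regime is concluded".
- **DATA ANALYSIS, Statistical methods planned:** "Primary analysis shall consist of applying the Anova single-factor acceptance test evaluating the change in waist circumference", at P=0.05. The result then goes straight to the decision on the primary objective. This section has no 1-inch condition and no timepoint.

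The quantity of interest also shifts between sections. Methodology and STUDY OBJECTIVES describe a before-after change, and EFFICACY lists "the change in patient waist circumference as a primary indicator". The synopsis Statistical Methods instead aims to "determine if the extent of circumference reduction in the test group is statistically significant over changes in the control group". Study configuration states "This study is designed as a single-arm study".

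Sample size uses a two-sample formula with 80% power, SD 1.50 inches and an effect of 1.0 inch, the same value as the success threshold.

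**The concern.** A primary success rule should let two analysts with the same data reach the same verdict. Here they need not. One could require 1 inch only, one could require 1 inch plus significance, and one could require significance only. Two analysts who both apply the two-part rule could still differ, because the inch might be judged on the treated-group mean, on the difference from control, or patient by patient. The sponsor analyses the data, so if the choice is made after results are seen, a positive claim would be open to challenge.

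A second gap follows. The only operating figure in the plan is 80% power, and it describes one of the two conditions. A reader cannot see how likely the trial is to meet its own full rule.

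**Working it through.** **Inputs.** From Sample size: Zα = 1.96 (two-sided 5%), Zβ = 0.84, d = 1.0 inch, σ = 1.50 inches, minimum 40 patients, 50 recruited. From STUDY OBJECTIVES: threshold 1 inch. Assumed, because the documents do not say: normal complete data (the least-favourable fill for dropouts is not modelled), equal SDs, 1:1 allocation, and a one-sample t-test if the design is single-arm.

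**Step 1: the plan's own figure.** 2 × (1.96 + 0.84)² × 1.5² / 1.0² = 2 × 7.84 × 2.25 = 35.28, so 36, against the stated 37. The smallest per-arm n with at least 80% t-test power is 37 (80.8%). The 80% is therefore the power to reject zero difference. It contains no requirement that the estimate reach 1 inch.

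**Step 2: can the rules disagree?** Take 25+25 and SD 1.5. The standard error of the difference is 1.5 × √(2/25) = 0.424, and a difference is significant from 0.853 inch (0.853/0.424 = 2.01). The second and third columns are mean losses in inches.

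| Case | Treated | Control | Difference | t | 1 inch only (treated mean) | Two-part, treated mean | Two-part, difference | ANOVA only |
|---|---|---|---|---|---|---|---|---|
| A | 1.20 | 0.60 | 0.60 | 1.41 | met | not met | not met | not met |
| B | 0.90 | 0.00 | 0.90 | 2.12 | not met | not met | not met | met |
| C | 1.30 | 0.40 | 0.90 | 2.12 | met | met | not met | met |

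In B and C, F = 2.12² = 4.50, p = 0.039, 95% CI 0.05 to 1.75. Case A separates the Methodology rule from the other two. Case B separates the ANOVA alone from the objectives. Case C shows two readings of the two-part rule disagreeing.

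**Step 3: how often?** Simulation with 1,000,000 replicates, true reduction 1.0 inch, no control change:

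| Design | Significant | Significant, treated mean below 1 inch | Full rule, treated mean | Full rule, difference |
|---|---|---|---|---|
| 20+20 | 54% | 15% | 39% | 48% |
| 25+25 | 64% | 21% | 43% | 50% |
| 37+37 | 81% | 33% | 48% | 50% |
| Single-arm, n=40 | 98% | 48% | 50% | n/a |

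The third column is the share of trials in which the ANOVA alone (or the t-test, if single-arm) says success and the two-part rule on the treated mean says failure. Significant data on which the treated-mean and difference readings disagree arise in 14% (20+20), 18% (25+25) and 23% (37+37) of trials.

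**Step 4: why about half.** If the true value equals the threshold, a symmetric estimate falls at or above it with probability 0.5. Adding the significance condition can only lower that. So with a true 1.0 inch, the full rule on the difference or on a single-arm mean cannot exceed about 50% at any n.

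**Step 5: control change.** The treated mean in a two-arm trial also depends on how much controls lose, which the documents do not give. Full rule judged on the treated mean, for control losses of 0.25 and 0.5 inch:

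- True difference 1.0: 50.3% and 53.5% at 20+20; 74.6% and 80.5% at 37+37.
- True treated mean 1.0: 27.7% and 15.9% at 20+20; 40.3% and 24.8% at 37+37.

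A per-patient reading cannot be computed, because no required proportion of patients is given.

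**The case against.** The strongest reply is that the Statistical methods section does not redefine success. It refers to the primary objective, and that objective is the two-part rule, so the ANOVA supplies significance and the objectives still supply the inch. This is a fair reading. A reader might infer a flat contradiction between the two sections, but the documents do not force one; the ANOVA-only verdict needs that section to be read alone. The reply does not say what must reach 1 inch, and it does not account for the Methodology sentence that rests success on the inch alone.

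Second, any rule that asks an estimate to reach its own true value passes at most about half the time, and Sample size claims only the usual power to reject the null. That stands. A reader might infer that the 80% is wrong on this ground; it is not, it is only incomplete.

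Third, a reader might take the 39% to 50% in the Step 3 table as the trial's chance of success. The documents do not support one such range. It needs zero control change, and its low end mostly reflects a separate problem, a per-arm n used as a total.

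Fourth, a reader might infer that the independent review looks only at significance, since Sample size mentions only that kind of conclusion. The Introduction has an independent statistical resource review the analysis that determines success on the primary and secondary objectives, so this inference fails.

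Finally, if the study is truly single-arm, the difference reading disappears. The choice between a group mean and individual patients remains, and so does the mismatch between the three statements.

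**Conclusion.** The point holds as a defect in the decision rule. Success is stated as 1 inch alone, as 1 inch plus significance, and, if the analysis section is read alone, as significance alone. On the most charitable joint reading the quantity that must reach 1 inch is still undefined.

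Under the Step 3 assumptions, the test is significant with a treated mean below 1 inch in about 15% to 33% of two-arm trials (20 to 37 per arm) and about 48% of single-arm trials at n=40. The full rule on the difference or on a single-arm mean is capped near 50% when the truth is 1.0 inch. For the treated mean in two arms no single figure can be given: it runs from about 16% to 81% over control losses of 0 to 0.5 inch and 20 to 37 per arm, depending also on whether the true difference or the true treated mean is 1.0.

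A reader might also infer an inflated false-positive rate. Requiring 1 inch on top of significance cannot raise the error rate above that of the test, so this does not follow. The consequence is an ambiguous success claim and a stated power that covers one of two conditions. It should be fixed before data are analysed.

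**What to change.** Settle two separate matters first: whether there is a control group, and whether 37 is a per-arm or a total number. Then:

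1. In the synopsis Methodology, STUDY OBJECTIVES and Statistical methods planned, state one identical two-part rule that names the single quantity that must reach 1 inch at 12 weeks. The before-after change in treated patients is closest to the present text of the first two, but neither says that it is a group mean, so the sponsor must specify that. If the sponsor prefers the between-group difference or a responder rule, declare it as a change of criterion.
2. In Statistical methods planned, replace the sentence that carries the ANOVA result straight to the objective with: the objective is met only if the named estimate is at least 1 inch and p<0.05 from the planned test, reported with its 95% CI. If the design stays single-arm, name the test of change, since a single-factor ANOVA then has no between-group factor.
3. In Sample size, say that 80% refers to significance only. Add the probability of meeting the full rule for the final design and n, with its assumptions on SD, control change and missing data.

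The cost is wording in four sections and one short calculation, with no extra patients, visits or measurements. The downside is a less favourable stated probability of success.

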After attachment of the handpiece, the operator selects which treatment type (US or RF) is to be done. The device then presents only two parameters for operator to adjust: the duration of the treatment, and the relative intensity of the applied energy. The duration can be selected from 10, 20, 30, or 40 minutes duration. The intensity is selected from a comparative rating Level of "1, 2, 3, or 4", with Level 4 being the maximum energy level the device can output and Levels 1 through 3 being at staggered levels less than the maximum. Once the settings are selected, the operator places the device into a Ready state. At this point, the handpiece is placed in contact with the skin and the operator presses a button on the screen to Activate the handpiece. The unit applies energy to the handpiece at the selected intensity Level and the unit begins to count down from the selected time duration. Generally, the operator allows the device to operate until the selected time elapses, at which point the device automatically returns to the Ready state and beeps to inform the operator the cycle is complete. The operator may also stop the treatment at any time, either by pressing the stop button on the screen or activating a separate emergency stop button located on the device. During treatment, the device monitors the temperature of the handpiece (and by contact, the temperature of the skin) via temperature sensors located in the handpiece and in direct contact with external metal surfaces of the handpiece that contact the skin. If excessive temperature is measured, the device halts operation of the handpiece. For the purposes of this study, the device will be set at a treatment time of 30 minutes and an intensity level of 4.

Adjunctive activities associated with the treatment will also be performed. These included conversation with the patient about what to expect during the individual treatments and overall outcomes of the entire regimen, as well as instructions to the patient at the conclusion of the study regarding care and proper lifestyle habits. All of these adjunctive activities are described in the operator's manual for the device, and the clinicians will be instructed on the presence of these consultative activities in the manual and the execution of these activities for the purposes of this study.

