**Post-Treatment Assessment (approximately 15 minutes):**

- The Post-Treatment assessing investigator observes the treated area for any redness, edema, swelling, or other indications specifically called for in the Anticipated Effects treatment record. The patient is asked for any unexpected sensations, for example sensations of high heat or of a "pins and needles" tingling effect in the tissue. These anticipated effects are documented in the treatment session record. Un-anticipated effects are recorded in the Adverse Event form.
- The patient is presented with the Stanford Pain Scale chart and asked to rate their overall pain and discomfort during the treatment. This is documented in the treatment session record.
- A waist circumference measurement of the abdominal region is made using the constant-tension tape measure. This measurement is recorded in the Post-Treatment Measurement record.
- The patient is provided with a study diary form, and instructed to document in the diary any unusual sensations, events, or bodily responses and to bring the form with them for the next visit.
- At the final treatment session only, the patient is provided with the Q-Post Survey to fill out.
- The patient is then scheduled for the next study session, and then excused.

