### **Sample size**

A total sample size of a minimum of 40 patients was established for this study. This number is based on

$$n = \frac{2 \cdot (Z_\alpha + Z_\beta)^2 \cdot \sigma^2}{d^2}$$

where:

$Z_\alpha = 1.96$ , based on a confidence of  $P=0.05$  (false rejecting of a true null hypothesis),  
 $Z_\beta = 0.84$ , based on a power of 80% (failure to reject a false null hypothesis),  
 $d = 1.0$  inch reduction in waist circumference as a meaningful/successful change in measurement,  
 $\sigma = 1.50$  inches, based on the evidence presented by a published study under similar treatment parameters and conditions reporting a typical response of 0.75 inches through the umbilical region and assuming some of the population may not respond at all.

The resulting calculation gives a population size of 37. Accounting for possible attrition and adding a generous margin of safety, a recruitment size of 50 individuals is arrived at. Review of the data analysis shall be conducted by an independent entity to confirm the handling and calculation of data, and the conclusions drawn from the data regarding statistical significance.

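### The rule for declaring that benefit outweighs risk has no objective benefit term and does not require the primary objective to be met

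*Combined protocol and SAP*

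**What the plan says.** STUDY OBJECTIVES sets two success rules.

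- **Primary.** The reduction must be at least 1 inch and statistically significant, and "a reduction in waist circumference of at least one inch must be demonstrated at a point of 12 weeks", counted from the final session.
- **Secondary.** This is labelled a safety objective, but its success is defined as a favourable balance of benefit and risk. The rule begins "Quantitatively, the benefit is regarded to outweigh the risk when" and lists three conditions. Condition 1 covers pain: "No patients report a pain rating of 4 or higher on the Stanford Pain Scale". Condition 2 allows nobody to have a side effect or abnormal finding once the last session ends. Condition 3 covers patient opinion: "No patient who was included in the Test group reports that the treatment regimen was unsuccessful".

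Other sections bear on this:

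- The EFFICACY section names change in waist circumference as the primary output and lists no other efficacy output.
- The synopsis (Methodology) ties study success to at least 1 inch of reduction at week 12.
- The Introduction has the sponsor determine success on the primary and the secondary objectives.
- Surveys are collected more than once. At Post-Treatment Assessment, "At the final treatment session only, the patient is provided with the Q-Post Survey to fill out". The FOLLOW-UP section adds surveys at weeks 1, 4 and 12.

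**The concern.** A statement that benefit outweighs risk should rest on evidence that the benefit occurred. Here the intended benefit is waist reduction, which is measured by tape, yet the tape result plays no part in the rule. Conditions 1 and 2 concern harm and tolerability. Condition 3 concerns benefit, but it is an opinion and is satisfied by the absence of negative reports.

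That opinion may be coloured by what patients are told. The adjunctive activities include "conversation with the patient about what to expect during the individual treatments and overall outcomes of the entire regimen". The rule does not say which survey item counts as a report of failure, or at which visit.

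At stake is a pre-specified claim containing the word benefit that could appear in the same report as a failed primary objective, with nothing in the plan to stop it.

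**Working it through.** **1. Is there a link to the waist result?** Setting each condition against the primary criterion:

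| Condition | What it uses | Uses waist change? |
|---|---|---|
| 1 | Pain rating, zero patients at 4 or higher | No |
| 2 | Side effects at the end of the final treatment, zero patients | No |
| 3 | Patient report that the regimen was unsuccessful, zero Test-group patients | No (opinion only) |

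No section makes the declaration conditional on the primary objective. Passing all three conditions after missing the inch is therefore formally possible. If meeting the primary were required, that combination would have probability 0.

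**2. The plan's own figure.** The plan gives no number for this rule. Its sample-size formula supplies the inputs used below: 2 × (1.96 + 0.84)² × 1.50² / 1.0² = 35.28, which rounds up to 36 against the stated 37. The difference does not affect this point.

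**3. How easily might the inch be missed?** The inputs from Sample size are SD 1.50 inches, a minimum of 40 completers, and a cited study "reporting a typical response of 0.75 inches through the umbilical region". Two assumptions are needed: that 0.75 inch is the true mean, and that the 1-inch criterion is judged on the observed group mean.

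- Standard error = 1.5 / √40 = 0.237.
- P(mean < 1) = Φ((1 − 0.75) / 0.237) = Φ(1.054) = 0.854.
- The same calculation gives 0.845 at n = 37 and 0.881 at n = 50.
- At an assumed true mean of 0.5 inch and n = 40, it gives Φ(0.5 / 0.237) = 0.982.

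The primary also requires statistical significance, which this calculation leaves out.

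**4. How easily might the rule pass?** If each of 40 patients independently has probability p of tripping any condition, the rule passes with probability (1 − p)^40. The values of p are assumptions.

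| p | Rule passes |
|---|---|
| 0.1% | 0.96 |
| 1% | 0.67 |
| 5% | 0.13 |
| 10% | 0.015 |

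For condition 3 alone, a normal distribution with mean 0.75 and SD 1.5 puts Φ(−0.5) = 0.309 of patients at no reduction. If a share q of those patients (assumed) report failure and nobody else does, condition 3 passes with probability (1 − 0.309q)^40.

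| q | Condition 3 passes |
|---|---|
| 0% | 1.00 |
| 1% | 0.88 |
| 5% | 0.54 |
| 10% | 0.29 |
| 25% | 0.04 |

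**5. The joint event.** The contradictory report needs a failed primary and a passed rule. Under the 0.75-inch assumption, the chance of missing the inch and also passing the rule cannot exceed 0.854, and it could be close to 0. The documents give no pain, side-effect or dissatisfaction rates that would narrow this range.

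**The case against.** The strongest reply has four parts.

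- **The rule does contain a benefit item.** Condition 3 asks about success and has zero tolerance: one negative report blocks the declaration. This stands. A reader might infer that the rule has no benefit term at all, and the documents do not support that. What is missing is an objective term.
- **The study-success label is protected.** The synopsis ties it to the inch, so passing the secondary rule cannot rescue a failed primary. This also stands. It does not stop the secondary declaration being made in its own right.
- **The contradiction may be rare.** Three zero-count conditions are hard to pass, and condition 3 tends to bite when the device underperforms. This is fair, and it limits the practical size. But strictness on pain and side effects is no evidence of benefit: a painless, harmless and ineffective device would pass conditions 1 and 2.
- **Missing 1 inch is not the same as no reduction.** With a true mean of 0.75 inch, SD 1.5 and n = 40, a two-sided one-sample t-test would find a change from zero about 87% of the time. This stands as arithmetic, though a before-after change does not by itself show a device effect, and the plan sets 1 inch as the meaningful amount.

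Two further inferences should be resisted. The Q-Post survey precedes the endpoint by 12 weeks, but the opinion need not come from it: FOLLOW-UP collects a week-12 survey, and condition 3 has no time limit. Nor can one rely on all patients knowing they are treated. Study configuration describes a single arm, while the title page, the synopsis and condition 3 itself imply a control. That conflict needs its own reconciliation, and waist change is absent from the rule under either design.

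**Conclusion.** The point holds in a limited form. The declaration that benefit outweighs risk has no objective benefit term and is not conditional on the primary objective, so the report could carry it alongside a failed primary. This follows from the text and needs no assumption.

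Its frequency cannot be computed from the documents. The 85% figure might be taken as the chance of a contradictory report, but it is only the chance that the observed mean misses 1 inch. It rests on an assumed true mean of 0.75 inch, SD 1.5, 40 completers and a criterion judged on the group mean. The 0.75 comes from a study whose title describes a low-intensity device, whereas this trial uses its device's maximum setting, so it may not carry over.

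Severity is minor to moderate: the primary analysis and the definition of study success are untouched, but a pre-specified claim is left without objective support.

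**What to change.** Keep the three conditions in the secondary objective and add a fourth: that the primary objective is met, meaning a waist reduction of at least 1 inch that is statistically significant at week 12. Add that, if it is not met, the pain and side-effect results are reported as tolerability only, with no benefit-risk claim. Condition 3 should stay, since removing it would drop a guard the plan already has. In the same edit, name the survey item and visit that supply condition 3.

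The cost is a sentence or two and no new data. There is no delay, because the plan already holds the analysis until the 12-week visits are complete. The downside is that the benefit-risk claim is lost whenever the primary objective fails, including when the reduction is real but smaller than 1 inch.
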